**CCI**

21. Patient has any of the following laboratory test results during Screening:

- a. Aspartate aminotransferase or ALT level  $\geq 2.5 \times$  the upper limit of normal (ULN)
- b. Alkaline phosphatase level  $\geq 2.5 \times$  ULN
- c. Total bilirubin level  $\geq 2 \times$  ULN (except for Gilbert Syndrome: direct bilirubin  $\geq 2 \times$  ULN)
- d. Potassium level  $< 3.0$  mEq/L; or  $> 10$  mEq/L
- e. Corrected serum calcium  $> 14.0$  mg/dL (3.5 mmol/L)
- f. Magnesium level  $< 1.0$  mg/dL

22. Patient is a woman who is pregnant or breastfeeding or planning to become pregnant while enrolled in this study or within 1 month after the last dose of NKTR-255 or within 2 months after the last dose of cetuximab.

23. Active brain metastases or leptomeningeal metastases patients with brain metastases are eligible if these have been treated and there is no radiographic evidence of progression for at least 4 weeks after treatment is complete (confirmed by the head imaging obtained within 28 days prior to study treatment). There must also be no requirement for immunosuppressive doses of systemic corticosteroids ( $> 10$  mg/day prednisone equivalents) for at least 4 weeks prior to study treatment. Stable dose of anticonvulsants is required within 14 days prior to study treatment. Treatment for central nervous system metastases may include stereotactic radiosurgery (eg, GammaKnife, CyberKnife, or equivalent) or neurosurgical resection. Patients who received whole brain radiation therapy are not eligible.

24. History of unstable hypertension and/or Screening blood pressure  $> 150/90$  millimeters of mercury (mmHg) (systolic/diastolic) with or without end organ damage; Screening blood pressure must be  $< 150$  mmHg for systolic blood pressure and  $< 90$  mmHg for diastolic blood pressure (by at least 1 and up to 3 observations taken during the Screening period).
25. Live, attenuated vaccines are prohibited within 30 days before the first dose of study drug (exception is made for vaccines against severe acute respiratory syndrome coronavirus 2 [SARS-CoV-2]; coronavirus disease 2019 [COVID-19]). For details, refer to Section 5.10.3.
26. Known current drug, alcohol, or tobacco abuse
27. Any condition including medical, emotional, psychiatric, or logistical that, in the opinion of the Investigator, would preclude the patient from adhering to the protocol

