## 1.2 Schedules of Events

**Table 1: Schedule of Visits and Assessments – Phase 1b (CRC and HNSCC; NKTR-255 Dose Escalation)**

Event a	Screening Period	Treatment Period																		Post-treatment Period					
		Run-in (1 week)			Cycle 1 (21-day cycle)						Cycle 2 (21-day cycle)						Cycle 3 (21-day cycle)			Cycle 4+ (21-day cycles)					
		Day	Day	Day	Day	Day	Day	Day	Day	Day	Day	Day	Day	Day	Day	Day	Day	Day	EOT b	60-day Follow-up c	Survival Follow-up c				
≤ 28d prior to Day 1 of Run-in Period		-7	-6	-4	1	2	3	4	5	8	10	15	1	2	3	4	8	10	15	1	4	8	15		
Windows (days)		+1			+1								+1						+1		+1		+7	±14	Every 3 months ±14 days
Screening Assessments																									
Informed consent		X																							
Inclusion/exclusion criteria		X																							
Demographics		X																							
Medical/cancer history		X																							
Medication/cancer therapy history d		X																							
HBV, HCV, HIV serology e		X																							
MRI f		X																							
General and Safety Assessments																									
Physical examination g		X	X		X						X							X			X		X	X	
Weight (kg) h		X	X		X						X							X			X		X		
Vital signs i		X	X		X	X	X	X	X	X	X	X	X	X	X	X	X	X		X		X	X		

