- a. All procedures and examinations should be performed before the administration of study drug(s) on dosing days, except as indicated. The acceptable visit window is + 1 day for Day 1. If scheduled visits or assessments coincide with a weekend or holiday, schedule at the next feasible date. Please contact the Medical Monitor to discuss any concerns about study visits or assessments that may fall out of the protocol-specified window because of unforeseen delays or other patient-specific circumstances. All out-of-window visits and procedures will incur a protocol deviation.
- b. The EOT visit should occur within 7 days after study treatment is discontinued, or before a new antineoplastic regimen has been initiated.
- c. Safety follow-up visit to occur 60 days after the last dose of study treatment. Survival follow-up visits will occur every 3 months from EOT.
- d. Includes previous immunotherapy, chemotherapy, targeted therapy, radiation therapy, prescription medications, over-the-counter medications, and herbal and dietary supplements.
- e. Patients with HNSCC must also have HPV and EBV status at Screening or provide historical assessment results.
- f. Brain MRI is only required for patients with a history of brain metastases. A standard-of-care brain MRI occurring prior to the 28-day screening window may be acceptable based on consultation with the Medical Monitor.
- g. See Section 7.13. Screening and End of Treatment physical examinations will be a complete physical examination. Symptom-directed physical examinations should be performed at the discretion of the Investigator to identify changes from baseline or to evaluate changes based on the patient's clinical symptoms during other clinic visits. The patient's height is measured at the Screening visit.
- h. The dose does not need to be recalculated for weight changes that are < 10% from baseline (Day -7).
- i. Vital signs to be recorded include temperature, pulse, respiration, systolic and diastolic blood pressure, and oxygen saturation (PaO2). PaO2 monitoring is required only at Screening and on dosing days. Collect vital signs before PK sample collection when both vital signs and PK samples are scheduled for the same timepoint, except EOI timepoint. CCI [REDACTED]  
[REDACTED]
- j. An echocardiogram or MUGA or nuclear scan for cardiac function and measurement of LVEF is required prior to dosing and may have been obtained within 60 days prior to C1D1.

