# CCI

## 4.2 Exclusion Criteria

Patients who meet any of the following criteria are ineligible:

1. Use of an investigational agent or an investigational device within 28 days before administration of first dose of study drug(s)
2. Patients who have an active, known, or suspected autoimmune disease. Patients requiring systemic treatment within the past 3 months or a documented history of clinically severe autoimmune disease that requires systemic corticosteroids or immunosuppressive agents (exceptions include any patient on 10 mg or less of prednisone or equivalent, patients with vitiligo, hypothyroidism stable on hormone replacement, Type I diabetes, chronic graft-versus-host disease, Graves' disease, Hashimoto's disease, alopecia areata, eczema, psoriasis, or with Medical Monitor approval).
3. History of allergy or known hypersensitivity to murine protein or study drug components
4. History of organ transplant that requires ongoing use of immunosuppressive agents
5. Patients who have been previously treated with IL-2 or IL-15

6. Patients with HNSCC who require treatment with anticoagulation therapy are not eligible. Use of warfarin for CRC, **CCI** [REDACTED] patients within 14 days of initiating study drug(s) is not permitted. Additional information about anti-coagulant therapy on treatment can be found in Section [5.10.3](#).
7. Known Grade 3 or 4 hypersensitivity reaction to cetuximab, history of allergy to red meat or tick bites, or history of positive test results for immunoglobulin E antibodies against cetuximab
8. Patient has had prior Grade 4 IRR to cetuximab
9. Unresolved toxicity from previous anti-cancer therapy, unless resolved to Grade  $\leq 1$  or baseline; or resolved to Grade 2 (with the exceptions outlined in the inclusion criteria or deemed clinically not significant, and approved by the Sponsor); or resulting from incomplete recovery from recent surgery (major)
10. Prior surgery or radiotherapy within 14 days of initiating study drug(s). Patients must have recovered from all acute radiation-related toxicities, not require corticosteroids, and have not had radiation pneumonitis.
11. Patients participating in observational studies should be discussed with the Medical Monitor to confirm eligibility.

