### **8.2 Tumor Imaging (Computed Tomography or Magnetic Resonance Imaging)**

Computed tomography (CT) with contrast or magnetic resonance imaging (MRI) (for patients who cannot tolerate CT contrast) will be obtained to document metastatic disease, identify target lesions as described in RECIST 1.1, and to assess response and disease progression. Imaging by CT scan with contrast or MRI will be performed at Screening, and approximately every 9 weeks during the treatment period regardless of cycle number or dose interruption.

Scans taken as part of standard medical practice up to 42 days prior to first dose of study treatment can be used for Screening. During the treatment, scans may be performed at timepoints other than every 9 weeks as clinically indicated to assess tumor progression. A standard-of-care brain MRI occurring prior to the 28-day screening window may be acceptable based on consultation with the Medical Monitor.

The text 'CCI' is displayed in a large, bold, red font, centered on a solid black rectangular background.

At Screening, a brain MRI is only required for patients with a history of brain metastases and should be followed as clinically indicated. Other scans may be included as clinically indicated.

For patients who stop study treatment in the absence of disease progression (eg, due to unexpected toxicity), scans should continue to be collected approximately every 9 weeks until disease progression or initiation of systemic anti-tumor therapy other than the study treatment (whichever is earlier) or unless patient withdraws consent.

The same imaging procedure and specifications (eg, contrast agent, scanner, slice thickness, etc.) used to define measurable target and non-target lesions must be used throughout the study for each patient.

Computed tomography scans may not be performed at sites or in countries where additional radiology approval is required, unless that approval is sought and granted.

The text 'CCI' is displayed in a red font, centered on a solid black rectangular background.

CCI

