## 6.6 Definitions

### Run-in period:

Eligible patients on combination therapy will receive cetuximab 400mg/m^2 IV as a loading dose during the study run-in period (Day -7). The run-in period therefore starts from the time the patient receives cetuximab and ends when the patient receives combination treatment of NKTR-255 +cetuximab.

**Study drug or study treatment:** Study drug or study treatment refers to NKTR-255 or cetuximab.

**Study day:** Study Day 1 (C1D1) is the first day that the combination treatment of NKTR-255 +cetuximab begins.

**Baseline:** Unless otherwise specified, the baseline value for each variable is the last non-missing value collected at the time (if collected) closest to, but prior to, the start of NKTR-255 administration. For triplicate ECG data, the record with three non-missing value will be considered as non-missing. If multiple measurements occur on the same day at the same time, or on the same day but the time is not available, the average of the measurements (for continuous data) will be considered the baseline value. When dosing times and/or observation times are not collected, it is assumed that protocol planned in-office assessments obtained on the day of the first dose of study drug are prior to administration of the first dose of study drug and therefore considered baseline values.

**Last known alive date:** The date of last known alive date will be derived for patients unknown to have died or known alive at the analysis cut-off by using following dates:

- Patient assessment dates (blood draws **CCI** [REDACTED], vital signs, performance status, ECG, tumor assessments, ECOG, or tumor biopsy dates)
- Start and end dates of anti-cancer therapies administered after study treatment discontinuation
- AE start or end date
- Concomitant medication start or end dates
- Last date of contact collected on the 'Survival follow-up' eCRF (do not use date of survival follow-up assessment unless status is 'alive')
- Study treatment start or end date
- Date of discontinuation for study participation on disposition eCRF pages (do not use if reason for discontinuation is lost to follow-up)

Only dates associated with actual examinations of the patient will be used in the derivation. Dates associated with a technical operation unrelated to patient status such as the date a blood sample was processed will not be used.

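### Exclusion 23 requires head imaging within 28 days before study treatment, but Table 1 footnote f and Section 8.2 allow an older brain MRI that cannot by itself meet that limit

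*Protocol*

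**What the plan says.** Exclusion 23 (Protocol Section 4.2) excludes active brain or leptomeningeal metastases. It allows treated brain metastases if there has been no radiographic progression for at least 4 weeks after treatment, "confirmed by the head imaging obtained within 28 days prior to study treatment". The criterion contains no exception and gives the Medical Monitor no role.

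The imaging instructions are elsewhere. Table 1 footnote f states: "Brain MRI is only required for patients with a history of brain metastases". Section 8.2 says the same: "At Screening, a brain MRI is only required for patients with a history of brain metastases and should be followed as clinically indicated". Both places then carry an identical allowance: "A standard-of-care brain MRI occurring prior to the 28-day screening window may be acceptable based on consultation with the Medical Monitor".

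Three other statements fix the dates:

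- The Screening column of Table 1 is headed by a limit of "28d prior to Day 1 of Run-in Period". Run-in starts with the cetuximab loading dose on Day -7 (Protocol Section 5.1.1).
- SAP Section 6.6 defines the term used in exclusion 23: "Study drug or study treatment refers to NKTR-255 or cetuximab".
- Section 8.2 has a general scan allowance: "Scans taken as part of standard medical practice up to 42 days prior to first dose of study treatment can be used for Screening".

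**The concern.** The two sets of instructions address the same scan in nearly the same patients and point different ways. Exclusion 23 makes recent head imaging a condition of entry. Footnote f and Section 8.2 let an older brain MRI stand after a conversation with the Medical Monitor, and neither refers back to exclusion 23 or says that newer imaging is still needed.

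Where the protocol wants discretion over an exclusion, it can write it into the criterion itself. Exclusion 2 ends its list of exceptions with "alopecia areata, eczema, psoriasis, or with Medical Monitor approval". Exclusion 23 has nothing comparable.

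What is at stake is patient safety and clean eligibility. A site or Medical Monitor relying on footnote f could accept the older MRI as sufficient and start treatment without the check for intracranial progression that exclusion 23 requires. Protocol Section 5.12 warns of possible pain and swelling at tumor sites, and of necrosis or bleeding of tumor tissue, with the combination. It is a reasonable inference, though not stated in the protocol, that such effects matter more if an intracranial lesion is progressing unrecognised. The case would also be an eligibility deviation that the protocol itself appeared to invite. SAP Section 7.2 classes deviations affecting a subject's safety as significant, so the rule needs to be unambiguous for that review too.

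**Working it through.** No design figure is involved. The check compares the texts and counts days. It is confined to Phase 1b, whose schedule is Table 1.

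**Inputs**

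| Item | Value | Source |
|---|---|---|
| Maximum age of head imaging | 28 days before study treatment | Protocol 4.2, exclusion 23 |
| Start of Screening window | 28 days before run-in Day 1 | Protocol Table 1 |
| First cetuximab dose | Day -7, the start of run-in | Protocol 5.1.1 |
| First NKTR-255 dose | C1D1, 7 days after the loading dose | Protocol Synopsis |
| Meaning of study treatment | NKTR-255 or cetuximab | SAP 6.6 |
| General standard-practice scan allowance | 42 days before first dose | Protocol 8.2 |

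**Step 1: count from first study treatment as the SAP defines it (Day -7).** The Screening window and the exclusion 23 limit both run back 28 days from the same day, so they coincide. An MRI from before the window is more than 28 days old and fails.

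**Step 2: count from the first NKTR-255 dose (C1D1).** The same MRI is more than 28 + 7 = 35 days old. It fails by a wider margin.

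The choice of anchor therefore does not rescue the allowance.

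**Step 3: how old may the MRI be?** The older-MRI sentence gives no maximum. The 42-day allowance in Section 8.2 may or may not extend to brain MRI; the text does not say.

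- If it does, the MRI may exceed the exclusion 23 limit by up to 42 − 28 = 14 days.
- If it does not, no upper limit is stated.

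**Step 4: does the allowance reach exclusion 23's patients?** The Screening brain MRI is required only where there is a history of brain metastases. Exclusion 23 lists stereotactic radiosurgery and neurosurgical resection among acceptable treatments, so it covers patients whose lesions were resected or irradiated. The two groups overlap almost entirely.

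**Step 5: can both texts be obeyed?** Yes, but only by adding something that neither states. Exclusion 23 asks for head imaging rather than MRI specifically, so an older MRI together with a head CT or newer MRI within 28 days would comply.

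**The case against.** The strongest defence is that the texts do different jobs. Exclusion 23 decides eligibility. Footnote f and Section 8.2 decide only whether the scheduled MRI must be repeated, say merely that an older one may be acceptable, and declare nobody eligible. Protocol Section 11.1 bars investigators from departing from the protocol without an amendment, apart from immediate hazards and administrative changes, so a permissive footnote cannot cancel an exclusion. On this view only a cross-reference is missing. It stands that the two can be reconciled; what does not follow is that a site would know to do so, since footnote f names the same scan and patients and is silent on further imaging.

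Three further arguments carry less weight.

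- **Different populations.** A history of brain metastases could be slightly broader than exclusion 23's group, for example a remote resected lesion. Since exclusion 23 names resection as a treatment, this leaves little room.
- **Deliberate discretion.** Protocol Section 7.12 also places Medical Monitor discretion over eligibility evidence outside the criteria, by allowing local laboratory results. But that section requires a full repeat set of central results before dosing. Footnote f has no such safeguard.
- **A looser window.** If Screening is taken to begin at consent, a pre-consent MRI could still fall within 28 days of dosing. Table 1 anchors the window to run-in, however, and Section 5.2.1 already accepts standard-of-care procedures done before consent within the assessment window, with no Medical Monitor step. On the Table 1 anchor, the allowance adds something only for MRIs that exclusion 23 rejects.

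On practical weight, exclusion 23 keeps other safeguards: 4 weeks without progression, no immunosuppressive steroid doses for 4 weeks, stable anticonvulsant dosing, and no whole brain radiation. SAP Section 2.0 also records that only Phase 1b patients were enrolled. Both points limit the consequences without removing the inconsistency.

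**Conclusion.** The concern holds. As written, footnote f and Section 8.2 permit reliance on a brain MRI more than 28 days old at Day -7, and more than 35 days old at C1D1, where exclusion 23 requires imaging within 28 days and allows no exception. The excess is up to 14 days if the 42-day allowance applies, and otherwise has no stated limit.

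This rests on the Table 1 anchor for the Screening window. The result is the same whether study treatment is counted from cetuximab or from NKTR-255. The documents do not give the number of patients affected; that it is small is an assumption.

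The point is minor and worth correcting for safety and eligibility. No endpoint, sample size or other statistical figure changes. With enrolment limited to Phase 1b, its remaining use is mainly in deviation review and in any further enrolment under this text.

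**What to change.** Either of two changes, made in both Table 1 footnote f and Section 8.2, is enough:

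1. Delete the sentence allowing an older brain MRI; or
2. Keep it and add: *This does not override exclusion 23; patients with brain metastases must still have head imaging (MRI or CT) within 28 days before study treatment.*

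The second keeps whatever legitimate use the older MRI has, for instance as a comparison scan. In either case, state in Section 8.2 that the 42-day allowance for standard-practice scans does not apply to this head imaging.

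The cost is wording in two places. A few patients would need the Screening brain MRI already scheduled in Table 1, or a head CT within 28 days, instead of relying on an older MRI.

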## 5.0 INVESTIGATIONAL PLAN

### 5.1 Overview

This study is a Phase 1b/2, open-label, multicenter, dose escalation, and dose expansion study in patients with R/R HNSCC, CRC, CCI [REDACTED].

#### 5.1.1 Phase 1b – Dose Escalation

The NKTR-255 starting dose will be 1.5  $\mu\text{g}/\text{kg}$ , which had no safety concerns as defined by pre-specified dose-limiting toxicities (DLTs) in the first cohort of the FIH study Protocol 18-255-02. The starting dose is based on the safety data from escalation cohorts and the RP2D determination from the FIH study. The starting dose will not be greater than the highest dose determined by the Safety Review Committee (SRC) to have no safety concerns in the FIH study.

[figure not shown]
After an initial cetuximab loading dose, patients will receive IV NKTR-255 q21d in combination with cetuximab weekly (Figure 2). Beginning with Dose Level 1, successive dose levels of at least 3 patients each will receive ascending doses of NKTR-255 until the MTD and/or RP2D is determined. Approximately 30 patients may be enrolled in the dose escalation phase of the study. A 2-parameter Bayesian logistic regression model (BLRM) employing the escalation with overdose control (EWOC) principle (Neuenschwander, 2008) will be used as a guide during the escalation phase of the study for dose level selection and for determination of the MTD and/or RP2D. Additional dose levels may also be opened to further explore the MTD and/or RP2D. For details, refer to Sections 5.8 and 5.9.

The first patient (a sentinel patient) of each escalating NKTR-255 dose level will be monitored for safety and tolerability for 7 days after the first dose of NKTR-255 before additional patients are dosed within the same dose level.

A composite of clinical information will be used to select the RP2D based on safety and tolerability, PK, CCI and optimal biological response. Additional patients may be enrolled to refine the RP2D, and a minimum of 6 patients will be required to define the RP2D.

Eligible patients will receive cetuximab 400  $\text{mg}/\text{m}^2$  IV as a loading dose during the study run-in period (Day -7). Thereafter, cetuximab 250  $\text{mg}/\text{m}^2$  IV will be administered weekly and NKTR-255 will be administered q21d. The DLT window is 21 days after the first dose of NKTR-255. Patients who achieve optimal response (partial response [PR] or complete response [CR] as determined by RECIST 1.1) after at least 1 tumor assessment, as determined by the Investigator and in consultation with the Medical Monitor, will be given the option to continue treatment with NKTR-255 as single agent for maintenance every 28 days (q28d) at the same dose as the patient's originally assigned dose.

CCI [REDACTED]

The logo consists of the letters 'CCI' in a large, bold, red sans-serif font. The letters are slightly overlapping, with 'C' on the left, 'C' in the middle, and 'I' on the right. The background is a solid black rectangle.

- Intermediate doses may be evaluated.
- No intra-patient dose escalation will be allowed.
- Enrollment into a new dose level with an escalating dose of NKTR-255 cannot begin until the DLT window has closed for at least 3 patients in the prior dose level. The DLT window is 21 days after the first dose of NKTR-255.
- The SRC will assess safety before opening dose escalation to the next level.
- The Sponsor's decision to declare the RP2D of NKTR-255 can occur at any given dose level based on safety, PK or CCI ██████ effects without reaching the MTD.
- Data from a minimum of 6 evaluable patients are required to define the RP2D.
- Dose reduction of NKTR-255 is not allowed during dose escalation within the DLT window. Outside of the DLT window in the dose escalation phase, and during dose expansion, dose levels of NKTR-255 may be reduced depending on the severity, duration, and frequency of toxicities observed at the previous dose level tested (the dose level may be de-escalated in order to characterize RP2D for a specific dose).
- The cetuximab dose may be reduced or adjusted based on review of available safety and tolerability data. Dose adjustment or discontinuation for cetuximab may be required based on emerging toxicities, and should follow the guidelines specified in this protocol and in the current local prescribing information for cetuximab.

CCI

